#### 9. Management of Analysis Data

#### 9.1 Covariates and Subgroups

#### 9.1.1 PLANNED COVARIATES

#### 9.1.2 SUBGROUPS

None are planned.

#### 9.2 Interim Analyses

No interim analyses are planned.

[figure not shown]
9.3 Handling of Early Termination Visit Information

[figure not shown]
9.4 Pooling of Study Centers

9.5 Missing Data

9.5.1 HANDLING OF MISSING DATE VALUES

9.5.1.1 Partial or Missing Dates

#### **10. Analysis Populations**

Analysis populations include the intent-to-treat (ITT) population, the per-protocol (PP) population, and the safety population. The statistical analysis of safety data will be performed on the safety population. The analysis of efficacy data will be performed on the ITT population and on the PP population to provide sensitivity analyses.

#### 10.1 Intent-to-Treat

The ITT population includes all randomized subjects. Subjects in the ITT population will be analyzed as randomized.

#### 10.2 Per Protocol

The PP population includes subjects in the ITT population subject who received at least one dose of IP who met all inclusion/exclusion criteria, and who did not incur a major protocol deviation. Protocol deviations will be assessed prior to database lock and unmasking. Subjects in the PP population will be analyzed as treated.

#### 10.3 Safety

The safety population includes all randomized subjects who have received at least one dose of the investigational product. Subjects in the safety population will be analyzed as treated.

#### **11. General Statistical Considerations**

11.1 Unit of Analysis

#### 11.2 Missing or Inconclusive Data Handling

Minimal data loss is anticipated and a need for imputation applied to missing values and/or other procedures (e.g., tipping point analysis) is not expected.

#### 11.3 Definition of Change Score

#### 12. Disposition of Subjects

Subject disposition will be presented in terms of the numbers and percentages of subjects who were randomized, completed the study, and discontinued from the study. Subjects who are not discontinued from the study will be considered study completers.

This information will be presented for the ITT, PP, and Safety populations. In general, percentages will be calculated using randomized subjects as the denominator (with any exceptions noted).

The reasons for study

discontinuation that will be summarized include AE, protocol deviation, administrative reasons (e.g., inability to continue, lost to follow up), Sponsor termination of study, subject choice, and other. A subject listing will be provided that includes the date of and reason for premature study discontinuation.

The number and percentage of subjects with major protocol deviations will be summarized by sequence, period, treatment ignoring sequence, and all subjects, for all randomized subjects. The protocol deviations that will be summarized include: Informed Consent, Inclusion / Exclusion and Randomization, Test Article / Study Drug Instillation and Assignment at Site, Improper Protocol Procedures at Site, Site's Failure to Report SAE / AE, Visit Out of Window, Subject's Non-compliance with Test Article, Subject's Use of Prohibited Concomitant Medication, Subject's Failure to Follow Instructions, and Other. A subject listing will be provided that includes the date and description of each deviation.

#### 13. Demographic, Body Habitus and Pretreatment Variables

#### 13.1 Demographic and Body Habitus Variables

The demographic and body habitus variables collected in this study include age, sex, race, ethnicity, height, and weight.

Age (years) will be summarized using continuous descriptive statistics. Further, age will be categorized as follows: <65 years and ≥65 years. Age will be reported in years and calculated using the following formula:

The number and percentage of subjects will be presented for age category, sex, race, and ethnicity by eye (OD and OS, separately).

A subject listing that includes all demographic variables for the ITT population will be provided.

#### 13.2 Pretreatment Variables

Baseline disease characteristics captured by the Schirmers test, IOP, and VA will be summarized for all subjects by eye.

#### 14. Medical History and Concomitant Medications

#### 14.1 Medical History

Non-ocular medical history will be summarized using discrete summary statistics and presented by treatment condition at the subject and event level by System Organ Class (SOC) and Preferred Term (PT) using the ITT population. Ocular medical history will be similarly summarized at the subject and event level. If a subject reports the same PT multiple times within the same SOC, that PT will only be reported once within that SOC. As with the PT, if a subject reports multiple conditions within the same SOC, that SOC will only be reported once.

Listings of medical history will be generated separately for ocular and non-ocular data.

#### 14.2 Concomitant Medications

Concomitant medications will be coded using WHO Drug Dictionary **Concomitant** and summarized to the therapeutic drug class (Anatomical Therapeutic Chemical [ATC] 4 classification) and preferred name. If the ATC 4 classification is not provided, the next lowest classification that is provided in the coding dictionary will be used. The preferred name will be defined as the active ingredient; if the active

**Confidential & Proprietary** 

ingredient is not provided or includes more than two ingredients (e.g., multivitamins) then the drug name will be summarized as the preferred name. Any uncoded terms will be summarized under the ATC classification and preferred name of "Uncoded."

Concomitant medications are defined as those medications listed as having been taken 1) prior to initiation of study drug administration and continuing for any period of time following the first administration of study drug or 2) at any time following the first administration of study drug.

Concomitant medications will be summarized using the ITT population by treatment-period. Ocular and non-ocular medications will be summarized separately. Medications will be tabulated for each treatment condition using frequencies and percentages. Subjects may have more than 1 medication per ATC text. At each level of subject summarization, a subject will be counted once if he/she reports 1 or more medications. Percentages will be based on the number of subjects in each treatment condition. Listings of concomitant medications will be generated separately for ocular and non-ocular data.

# 15. Dosing Compliance and Treatment Exposure

#### 15.1 Dosing Compliance

An Investigator will be on-site for dosing and on-call throughout the two-day duration of the study; thus, significant percentages of major deviations as a result of dosing compliance are not expected.

#### 15.2 Treatment Exposure

Extent of treatment exposure for subjects will be calculated in days using the following:

Extent of Exposure (days) = Date of completion/discontinuation – date of Visit 2 (Day 1) + 1

Extent of treatment exposure for subjects who were lost to follow-up will be calculated in days using the following:

Extent of Exposure (days) = Date of last recorded visit – date of Visit 2 (Day 1) + 1

[figure not shown]
The presentation of extent of treatment exposure will use the safety population. A subject listing of treatment exposure will also be produced that will include overall exposure.

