Study Population	Approximately 50 subjects with DED, ages 18 to 70 years, are expected to be enrolled in the trial.
Study Conduct	
This clinical trial will have 6 visits, 2 in the Screening period (Visit 1a for medical screening and Visit 1b for DEC screening) and 4 visits in the Treatment periods. The first treatment period (Visits 2 and 3) will begin after at least a 7 to 14 day wash out post-screening Visit 1b. At Visit 2, subjects will be randomized to determine the order in which they will receive reproxalap or vehicle treatment. Subjects will receive the same study treatment on two consecutive days at Visit 2 (4 times) and Visit 3 (2 times). After a washout period of 7 to 14 days, subjects will return to the clinic for Treatment Period 2 (Visits 4 and 5) and cross over to receive the other randomized treatment on two consecutive days at Visit 4 (4 times) and Visit 5 (2 times).
 
Conjunctival redness will be assessed by trained study staff, whereas ocular dryness, itching, discomfort, burning, grittiness and stinging will be assessed by subjects [REDACTED] at treatment visits. Visit 2 and 4 will not include DEC exposure. Schirmer's test will be conducted at Visit 2 and 4. Visit 3 and Visit 5 will include DEC exposure and assessment of symptoms before and during exposure to DEC.
 
Safety endpoint assessments will be performed throughout the study. Adverse events and concomitant medication will be recorded (refer to Schedule of Assessments).
 
I. Visit 1a: Medical Screening (Day -21 to -8)
 
All subjects will undergo a medical screening visit (Visit 1a), including written informed consent, demographics, medical/medication and ocular history. Corneal fluorescein staining and urine pregnancy (for all female subjects) test will be performed.
 
II. Visit 1b: DEC Screening (Day -14 to -7)
 
Medical/medication and ocular history will be updated for each subject. SVA and SLE will be performed pre- and post-DEC. IOP will be performed post-DEC. Vehicle will be administered in the clinic approximately 5 minutes prior to the DEC entry and after 45 min in the DEC. Staff-assessed conjunctival redness will be performed approximately -10 (+1) and -5 (+1) minutes pre-DEC entry and approximately at 10, 20, 30, 40, 55, 65, 75, 85 and 90 minutes while in the DEC. Conjunctival redness will also be performed post-DEC (1 time within 15 minutes). Schirmer's test (baseline) will be performed prior to DEC entry. Ocular itching score and all VAS ocular symptoms will be performed pre- and post-DEC. VAS assessments for ocular dryness, discomfort, burning, grittiness and stinging will be performed approximately -12 (+1) and -7 (+1) minutes prior to DEC entry

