9. STUDY DESIGN

9.1. Overall Study Design

[figure not shown]
This is a randomized, double-masked, vehicle-controlled, crossover clinical trial to assess efficacy and safety of 0.25% reproxalap ophthalmic solution compared to vehicle in subjects with dry eye disease in a DEC.

This clinical trial will include 6 visits, 2 in the Screening period (Visit 1a for medical screening and Visit 1b for DEC screening) and 4 visits in the Treatment periods. The first treatment period (Visit 2 and 3) will begin after at least a 7 to 14 days of wash out period post-screening Visit 1b. At Visit 2, subjects will be randomized to determine the order in which they will receive Reproxalap and vehicle treatment. Subjects will receive the same study treatment at Visit 2 (4 times) and Visit 3 (2 times), which will be scheduled on consecutive days. After a washout period of 7 to 14 days subjects will return to the clinic for Treatment period 2 (Visit 4 and 5) and cross over to receive the other treatment at Visit 4 (4 times) and Visit 5 (2 times) scheduled on consecutive days.

Visit 2 and Visit 4 will not include DEC exposure. Schirmer's test will be conducted at these visits. Visit 3 and Visit 5 will include DEC exposure and assessment of symptoms before, and during exposure to DEC). Conjunctival redness will be assessed by trained study staff, whereas ocular dryness, itching, discomfort, burning, grittiness and stinging will be separately assessed by subjects [REDACTED].

Safety endpoint assessments will be performed throughout the study. Adverse events and concomitant medication will be recorded at each visit.

Figure 9-1 Study Design

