11. STUDY PRODUCT AND TREATMENT SEQUENCE

11.1. Study Product and Treatment

The following products will be used in the study:

Product A: 0.25% Reproxalap Ophthalmic Solution (reproxalap) (Manufactured by Aldeyra Therapeutics, Inc.).

Product B: Vehicle Ophthalmic Solution (vehicle) (Manufactured by Aldeyra Therapeutics, Inc.)

Study treatment (reproxalap or vehicle) will be dosed topically in both eyes (1 drop in each eye). Study treatment will be administered 4 times (Dose 1, Dose 2 [3 hours post dose 1], Dose 3 [30 min post Dose 2] and Dose 4 [30 min post Dose 3] at Visit 2 and Visit 4. Study treatment will be administered 2 times (Dose 1 [administered approximately 5 min Prior to DEC entry] and Dose 2 [administered approximately 45 min into the DEC session]) at Visit 3 and Visit 5.

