12.6. Visit 4 - Baseline Treatment Visit

Subjects will return to Visit 4 after 7 to 14 days of Visit 3, and undergo the same procedures as Visit 2.

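### The exposure formulas printed in SAP 15.2 count calendar time, washout included, so on the nominal schedule a completer shows 11 days against 4 randomized dosing days (2 per product)

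*SAP*

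**What the plan says.** SAP 15.2 (Treatment Exposure) prints two formulas. For completers and discontinued subjects: "Extent of Exposure (days) = Date of completion/discontinuation – date of Visit 2 (Day 1) + 1". For subjects lost to follow-up: "Extent of Exposure (days) = Date of last recorded visit – date of Visit 2 (Day 1) + 1". Some content after the second formula is not shown. The readable text resumes by assigning the presentation to the safety population, and adds: "A subject listing of treatment exposure will also be produced that will include overall exposure".

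The dosing schedule is in the protocol. For period 1, Section 5 says: "Subjects will receive the same study treatment on two consecutive days at Visit 2 (4 times) and Visit 3 (2 times"). For period 2, subjects "cross over to receive the other randomized treatment on two consecutive days at Visit 4 (4 times) and Visit 5 (2 times"). Section 11.1 confirms four administrations at Visits 2 and 4 and two at Visits 3 and 5, one drop in each eye. Between the periods no product is given. Section 9.1 says: "After a washout period of 7 to 14 days subjects will return to the clinic for Treatment period 2". Section 12.6 says: "Subjects will return to Visit 4 after 7 to 14 days of Visit 3". Section 12.7 places study exit at Visit 5.

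The visit table in SAP 5.1 puts Visits 2, 3, 4 and 5 on Days 1, 2, 10 and 11.

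**The concern.** In a parallel-group trial with continuous dosing, last date minus first date plus one is a fair measure of exposure. Here each subject takes two products, each on two days, with an undosed gap between them. A single span from Visit 2 to exit counts the gap as exposure and runs the two products together.

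The exposure summary exists to let a reader judge the safety tables. SAP 10.3 analyses the safety population as treated, protocol 15.4.3 presents safety data by treatment received, and SAP 17 summarizes treatment-emergent events by treatment-period. A value that covers both products cannot be set beside those tables, because it does not say how much reproxalap or vehicle anyone received. The completer case applies to nearly every subject, since SAP 11.2 expects little data loss.

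**Working it through.** There is no printed exposure figure to reproduce, so the check applies the SAP's formula to the documents' own schedule.

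**Inputs**
- Visit 2 = Day 1, Visit 3 = Day 2, Visit 4 = Day 10, Visit 5 = Day 11, with no Day 0 (SAP 5.1).
- Completion = Visit 5 (protocol 12.7).
- Randomized dosing at Visits 2, 3, 4 and 5 only, with 4 + 2 = 6 administrations per eye of each product, 12 in all (protocol 11.1).
- Washout of 7 to 14 days (protocol 9.1 and 12.6).
- The vehicle given at Visit 1b is before randomization. It lies outside both the formulas and this count.

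**Completer, nominal schedule**
- Formula: 11 − 1 + 1 = 11 days.
- Dosing days: Days 1, 2, 10 and 11 = 4, of which 2 are on each product.
- Ratio: 11 / 4 = 2.75.
- Undosed days: Days 3 to 9 = 7, and 7 / 11 = 64%.

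**Completer, across the permitted washout.** The documents allow two ways of counting.

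| Reading | Visit 4 | Visit 5 | Formula value | Value / 4 dosing days | Undosed days |
|---|---|---|---|---|---|
| Visit 4 = Visit 3 + 7 to 14 days | Day 9 to 16 | Day 10 to 17 | 10 to 17 | 2.5 to 4.25 | 6 to 13 (60% to 76%) |
| 7 to 14 full undosed days between visits | Day 10 to 17 | Day 11 to 18 | 11 to 18 | 2.75 to 4.5 | 7 to 14 (64% to 78%) |

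The first reading takes protocol 12.6 literally. The second fits the stated trial length of about 19 to 39 days: with Visit 1a on Day −8 to −21 and no Day 0, the total is 8 + 11 = 19 to 21 + 18 = 39. The first reading gives 8 + 10 = 18 to 21 + 17 = 38. Because the stated length is approximate, it does not settle the matter. On either reading, two on-schedule completers with identical dosing can differ by 7 days (17 − 10 or 18 − 11).

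**Withdrawn at Visit 4 before dosing.** Protocol 12.1 takes a COVID-19 swab at the start of Visit 4, and 13.2.5 withdraws a subject who tests positive, so the case can arise. On the nominal schedule, with withdrawal dated to that visit:
- Formula: 10 − 1 + 1 = 10 days. The two formulas agree, because the exit date is also the last visit date.
- Share of a completer's value: 10 / 11 = 91%.
- Actual dosing: 2 of 4 dosing days and 6 of 12 administrations per eye, all of one product. If the sequence was vehicle first, the subject has had no reproxalap.

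So the reported value can differ when dosing is the same, and can be nearly the same when dosing is halved.

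**The case against.** The strongest reply is that SAP 15.2 is incomplete as published. Content is missing directly after the second formula, and the next readable text has the listing include overall exposure. That word suggests, without proving it, that a breakdown by period or product stands beside the total. The printed formulas may then be only the overall line. This stands in part. A reader might infer that the SAP has no by-product exposure display, or that both formulas must be struck out. The documents support neither inference. They support only that the two printed formulas cannot yield a by-product value and that the label on them is wrong for this design.

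A second reply is that dosing is fixed and given in clinic, so departures would appear in the deviation summaries of SAP 12, which include study drug instillation and assignment and are shown by sequence, period and treatment. That is true and limits the practical harm, but it does not correct the value printed under the exposure title. The as-treated rule in SAP 10.3 does not correct it either.

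A third reply is that no inference rests on the value. This stands. The readable SAP has no exposure-adjusted event rate, and SAP 17 reports event counts and subject percentages. A reader might infer that adverse event percentages or the efficacy results are affected; they are not.

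A reader might also infer that the two formulas conflict for a subject who gives notice between Visits 3 and 4. That would require the discontinuation date to be the day of notice, which the documents do not define. A last-visit rule for subjects lost to follow-up is in itself reasonable.

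**Conclusion.** The point holds for the two printed formulas. What they call extent of treatment exposure is calendar time since the first randomized dosing visit, with the washout and both products included. On the nominal schedule a completer shows 11 days against 4 dosing days, 2 per product. Across the washout window the value is 10 to 17 or 11 to 18 days, depending on the reading. To quote either range as the only one would claim more than the documents support, but the 7-day spread is common to both. A subject withdrawn at Visit 4 before dosing shows 10 days on the nominal schedule after receiving one product.

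These figures assume that completion is dated to Visit 5 and, in the early-exit case, that withdrawal is dated to Visit 4. The consequence is limited to one descriptive summary and one listing. Severity: minor.

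**What to change.** Derive post-randomization exposure from the dosing records, by product actually received, as:
- number of dosing days (planned: 2 per product);
- number of administrations (planned: 6 per eye per product).

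Present reproxalap and vehicle separately on the safety population. If the calendar span is kept, label it *duration of study participation (time since first randomized dose)*. If the part of SAP 15.2 that is not shown already contains a by-product or by-period derivation, keep it and relabel only the printed formulas.

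The cost is SAP wording plus one table shell and one listing shell. Dosing is done in clinic and protocol Section 17 requires dosing records to be kept, so no new data are needed. The change does not touch dosing, the efficacy tests or the adverse event percentages.

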#### 16. Efficacy Analyses

#### 16.1 Analysis of the Primary Efficacy Endpoint(s)

There are two primary efficacy endpoints: 1) the Schirmers test score; and 2) the conjunctival redness score. The primary endpoints will be assessed using mixed model repeated measures (MMRM).

For any model, effects other than treatment and baseline with p values of 0.1 or greater may be removed optionally without consideration of convergence.

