15. STATISTICAL CONSIDERATIONS

15.1. Statistical Plan

A statistical analysis plan (SAP) detailing the intended statistical analysis of the study data will be prepared as a separate document and finalized before database lock. Any deviation from the SAP will be described and justified in the final report, as appropriate. The procedure for accounting for missing, unused and spurious data will be included in the SAP. [REDACTED]

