#### 6. Study Treatments

#### 6.1 Method of Assigning Subjects to Treatment Condition

Before the initiation of study at Screening Visit 1a, each subject who provides written and informed consent will be assigned to a screening number. All screening numbers will be assigned in strict numerical sequence at a site and no numbers will be skipped or omitted. Each subject who meets all the inclusion and none of the exclusion criteria at Visit 1a/b and Visit 2 will be assigned a randomization number at the end of Visit 2. The Interactive Web Response System (IWRS) will be used to assign all randomization numbers.

Randomization and kit numbers will be assigned automatically to each subject as they are entered into the IWRS.

The sequence in which subjects receive investigational product (reproxalap or vehicle) will be determined by randomization.

Randomization of subjects to one of the treatment sequences will be based on the randomization scheme.

Subjects will be randomized to one of two sequences: AB or BA.

Sequence	Treatment Period 1	Treatment Period 2
AB	Reproxalap	Vehicle
BA	Vehicle	Reproxalap

The randomization schedule will use block randomization, such that there will be an approximately equal number of subjects assigned to each of the two treatment sequences. Both the randomization number and the dispensed study drug kit number(s) will be recorded on the subject's source document and eCRF. The Sponsor, investigators, and study staff will be masked during the randomization process and throughout the study.

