#### 7. Sample Size and Power Considerations

Approximately 160 subjects with dry eye disease will be screened in order to randomize and realize study completion in approximately 50 subjects. Approximately 25 subjects will be assigned to one of two (2) treatment sequences, namely, AB (reproxalap then vehicle) or BA (vehicle then reproxalap).

In order to account for dropout and to assess safety and the other secondary endpoints, a total of 50 subjects will be randomized.

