Creation and validation of the EDC system and management of the data will be conducted. Methods used to ensure the quality and integrity of the data will be documented in the DMP, which will be approved by the Data Management provider and the Sponsor.

All analyses outlined in this document will be carried out after the following have occurred:

- All data management requirements are met according to standard operating procedures (SOP), including data entry, performance of edit and validation checks, documentation and resolution of data queries, and database lock with written authorization provided by appropriate
   and Aldeyra Therapeutics, Inc. personnel;
- Protocol deviations have been identified and status defined (major/minor deviations);
- Analysis populations have been determined; and
- Randomized treatment codes have been unmasked.

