#### 16.3 Multiplicity Considerations

P-values for the main effect of treatment will be ordered for the primary endpoints and Hochberg's procedure for multiplicity control will be used.

No type I error control will be utilized for exploratory endpoints. Thus, exploratory comparisons are considered hypothesis generating.

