#### 19. Additional Analyses

Additional analyses other than the planned analyses described herein may be conducted as ad-hoc analyses. All ad-hoc analyses will be identified in the CSR. The intent of any such analyses would be to better characterize treatment effects.

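### SAP 16.1 lets non-significant effects be dropped optionally from the primary models, and no visible text says whether the full or the reduced fit supplies the treatment p-value for Hochberg's procedure

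*SAP*

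**What the plan says.** SAP 16.1 names a mixed model for repeated measures (MMRM) for Schirmer's test and for conjunctival redness. It continues: "For any model, effects other than treatment and baseline with p values of 0.1 or greater may be removed optionally without consideration of convergence". The sentence applies to every model, so it covers both primary analyses, their per-protocol repeats, and the analogous secondary models of SAP 16.2.

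SAP 16.3 says: "P-values for the main effect of treatment will be ordered for the primary endpoints", and applies Hochberg's procedure to them. It does not say which fit those p-values come from.

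Protocol 15.4.1 describes a crossover MMRM for each primary endpoint. The visible part contains no removal rule. For redness it names baseline as a covariate and errors correlated by eye; the rest of the Schirmer sentence and the list of sensitivity analyses are blacked out. SAP 9.1.1 (planned covariates) is also empty in the public copy.

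Three visible rules bear on reporting:
- Protocol 15.1: "Any deviation from the SAP will be described and justified in the final report, as appropriate".
- SAP 19: "All ad-hoc analyses will be identified in the CSR".
- Protocol 14.1: the final report will narrate the statistical procedures that were used.

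**The concern.** Hochberg's procedure takes one defined p-value per primary endpoint. SAP 16.1 permits more than one whenever an effect other than treatment or baseline has p of 0.1 or more. With k removable effects there are up to 2^k possible fits: 2, 4, 8 or 16 for k = 1 to 4.

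The rule is not a convergence fallback, because the sentence sets convergence aside. It is not an algorithm either: a mandatory rule with a stated order would at least give a single result.

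SAP 8 lists, among the conditions for starting the analyses, "Randomized treatment codes have been unmasked". That order is ordinary. Combined with an optional rule, it lets the choice of fit be made with both treatment results in view.

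A reduced primary fit is allowed by the SAP, so it is neither a deviation under Protocol 15.1 nor an ad-hoc analysis under SAP 19. What is at stake is whether a reader can verify that the reported primary p-value was fixed in advance.

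**Working it through.** The plan gives no figure to reproduce on this point. The calculation below shows scale only.

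**Inputs from the documents.** Removal threshold 0.1 (SAP 16.1). A total of 50 randomized (SAP 7). Allocation: "Approximately 25 subjects will be assigned to one of two (2) treatment sequences" (SAP 7), with blocks giving an "approximately equal number of subjects assigned to each of the two treatment sequences" (SAP 6.1). On dropout: "Minimal data loss is anticipated" (SAP 11.2).

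**Assumptions, none in the documents.** Period is the only removable effect. Two-sided 5% level. Within-subject correlation ρ of 0.3–0.85. Period effect of 0 or 0.25 SD. Unequal splits of 28/22 and 30/20. Eye and time-point structure is not modelled.

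**Model.** Let m1 and m2 be the mean period-1-minus-period-2 differences in sequences AB and BA, with n = n1 + n2. Each difference has SD √(2(1 − ρ)).
- Full fit (period kept): estimate (m1 − m2)/2, t with n − 2 = 48 df.
- Reduced fit (period dropped): estimate (n1·m1 − n2·m2)/n, t with n − 1 = 49 df.
- Reduced minus full = [(n1 − n2)/n] × (m1 + m2)/2, that is, the imbalance times the estimated period effect.

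**How often the option is open.** With no period effect, period has p ≥ 0.1 in 90% of trials. With 0.25 SD and ρ = 0.3, the SE is √1.4/√50 = 0.167 and the noncentrality is 0.25/0.167 = 1.49, against a critical value of 1.68. That gives about 57%. Simulation gives 57–58% at ρ = 0.3, falling to 6–7% at ρ = 0.85.

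**How far the estimate moves.** At 25/25 the imbalance is zero, so the estimate does not move. At 28/22 the factor is 6/50 = 0.12, and at 30/20 it is 10/50 = 0.20. In trials where a 0.25 SD period effect is missed, its estimate is by selection smaller than 0.25 SD. The simulated mean shift is 0.012–0.016 SD at 28/22 and 0.020–0.028 SD at 30/20, which corresponds to mean period estimates of 0.012/0.12 = 0.10 to 0.028/0.20 = 0.14 SD.

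**Single-endpoint type I error** when the smaller p-value is taken whenever removal is allowed (the full fit alone holds about 0.05):

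| Split | Type I error | Period effect |
|---|---|---|
| 25/25 | 0.050–0.051 | 0 or 0.25 SD |
| 28/22 | 0.051–0.054 | 0.25 SD |
| 30/20 | 0.052–0.059 | 0.25 SD |

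A period effect is not needed for this. With none, the figure is 0.0575 at 30/20.

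**Hochberg over two endpoints** (endpoint correlation 0–0.5 assumed; reject both if both p ≤ 0.05, otherwise the smaller if ≤ 0.025). Family-wise error is 4.8–5.0% with period kept. With the rule applied, mechanically or optionally, it is 4.8–5.2% at 25/25, 4.9–5.5% at 28/22 and 5.1–6.1% at 30/20.

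**How often the two fits fall on opposite sides of 5%** for one endpoint while removal is allowed:

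| Split | No treatment effect | True effect, 50–80% power |
|---|---|---|
| 25/25 | at most 0.15% | at most 0.5% |
| 28/22 | at most 0.8% | at most 3.0% |
| 30/20 | at most 1.3% | at most 5.0% |

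**The case against.** **Redaction.** The model detail is blacked out, and the reference to convergence suggests that a convergence rule stands nearby. A reader might infer that the SAP never names a primary fit; the documents do not support that. A full-model analysis may be planned in the hidden text. What stands is narrower: the visible sentence permits optional removal from any list, and a hidden effect list or sensitivity analysis would not by itself say which fit is primary. Only an express limit on the sentence would.

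**Disclosure.** A reader might infer that the report could conceal the choice. Protocol 14.1 points the other way: removing model terms is a statistical procedure used, so the narrative should mention it. What remains is that no visible rule requires the result of the other fit to be shown.

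**Size.** At the planned allocation the error rate barely moves. The larger figures need splits that sit poorly with block randomization and minimal data loss. This objection stands. Period itself is an inference from the crossover design; no visible passage lists it as a model effect.

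**Bias mistaken for shift.** It is tempting to quote 0.25 × 6/50 = 0.03 SD and 0.25 × 10/50 = 0.05 SD as the change caused by dropping period. Those are the reduced estimate's biases against the truth. In the same selected trials the full estimate is biased too, by about 0.014–0.018 and 0.023–0.030 SD, so the change between fits is roughly half.

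**A bounded rule.** The threshold is fixed, treatment and baseline are protected, and the rule was written in advance. That limits the discretion without removing it.

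**Conclusion.** The point holds as a minor gap in pre-specification. SAP 16.1 makes removal optional in both primary models, and no visible text says which fit's treatment p-value enters Hochberg's procedure. Unmasking before analysis is not itself a fault, and the documents do not support a claim of material type I error inflation.

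If period is the only removable term, the effect at 25/25 is practically nil. Under the stated assumptions single-endpoint error stays below 0.06 even at 30/20. The illustration leaves out eyes and time points, and more removable effects would mean more fits to choose from. The size for the real effect list therefore cannot be determined from the public text, in either direction. The multiplicity argument concerns the two primary endpoints only.

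**What to change.** Replace the sentence in SAP 16.1 with:

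*The primary models retain all pre-specified effects regardless of their p-values, and this full model supplies the treatment p-value for Hochberg's procedure; any reduced model is a labelled sensitivity analysis reported beside it.*

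Leave any existing convergence rule in place; a new covariance sequence is not needed and might duplicate or contradict redacted text. The same wording could be used for the secondary models for consistency, but the multiplicity argument does not require it.

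The cost is one SAP sentence and a few degrees of freedom spent on non-significant effects (one, 48 against 49, in the period-only illustration). The exact number depends on the redacted effect list.
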